Photo-novella, or the use of photographs to tell a story, has been used as a group intervention (photovoice) and as an individual narrative intervention. Photographs as a voice or narrative have been found in a recent systematic review to be effective in participant empowerment, community change, knowledge acquisition, and reaching policymakers.

Digital Stories visually represent first-person narratives that utilize present-day digital culture. Digital stories ask participants to tell a story by creating a short (3-minute) autobiographical vignette synthesizing written text, still and moving imagery, voice, and sound. Digital stories include multiple sensory contexts (e.g., text, spatial, visual, verbal,

and gestures) to convey meaning and can be interpreted on different levels by storytellers and listeners. In a review of digital stories for health promotion, digital stories were found to improve confidence, motivation, behavior change, and/or social change.

At the end of the pilot study, we will provide a voluntary space as a gallery for the critical narratives to be displayed and open to the public. The gallery will be optional for participants who wish to display their critical narratives.

OBJECTIVES:

Our primary objective is to identify the potential use of critical narratives as an elicitation strategy to increase empowerment (e.g., increase in self-esteem), and improve mental health symptoms (e.g., decrease in depression and anxiety, and increase in psychological well-being) in vulnerable populations of SGM individuals of color living with depression. Our secondary objective is to assess the feasibility, acceptability, and appropriateness of critical narratives (photo-novella and digital storytelling) for SGM EA of color. Our specific aims are:

1. Examine the experiences of discrimination and acceptance of SGM EA of color living with depression in their community,
2. Evaluate the impact of CN on empowerment (e.g., self-esteem) and mental health outcomes (depression, anxiety, and psychological well-being) of SGM individuals of color.
3. Understand the acceptability, appropriateness, and feasibility of critical narrative development as a strategy for SGM EA of color.

Outcomes

The study has two primary outcomes addressed in Aim 1 and Aim 2.

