To identify the potential use of critical narratives to elicit empowerment, we will first examine the current experiences of SGM EA of color. Therefore, aim 1 will examine the experiences of stigma (e.g., discrimination) and acceptance of SGM EA of color living with depression and how this may impact mental health treatment seeking in the community. We will conduct in-depth interviews with participants at baseline using an in-depth interview protocol which will include open-ended questions to examine the unique experiences of SGM EA living with multiple marginalized identities (sexual and gender minority, person of color, and living with a mental illness). Utilizing a semi-structured interview protocol, participants will be asked questions about how they identify (i.e., racially/ethnically, sexual identity, and gender identity), their experiences as an LGBTQ+ person in their culture, and their experiences as SGM EA of color in the United States.

Aim 2 will evaluate the impact of CN assignment (photo-novella or digital storytelling) in its ability to address the primary outcomes of:

- 1) Mental health measures:
 - a. decrease depression symptoms utilizing the Patient Health Questionnaire (PHQ-9),
 - b. reduce anxiety symptoms utilizing the Generalized Anxiety Disorder-7 (GAD-7),
 - c. increase psychological well-being using the Flourishing Scale,
- 2) Empowerment measures:
 - a. increase self-esteem using the Rosenberg Self-Esteem Scale,
 - b. increase empowerment utilizing the Rogers empowerment scale,

We will also note the effect of CN assignment to address secondary outcomes of:

- 3) Stigma as a known barrier to mental health treatment seeking:
 - a. decrease internalized mental health stigma using internalized stigma of mental illness (ISMI-9) scale.
 - b. decrease in intersectional minority stress using the LGBTQ+ POC Microaggressions Scale-Brief (LGBTQ+ PCMS-B).
- 4) Intentions to seek care and social support:
 - a. increase in positive attitudes to seeking mental health care using the Attitudes Toward Mental Health Treatment (ATMHT) scale as a secondary outcome of increased empowerment.
 - b. increase in intentions to seek out social support as a secondary outcome of increased empowerment.
- 5) Social Connection
 - a. Increase in the general sense of belonging using the General Belongingness Scale (GBS)
 - b. Increase in perceived social support using the Multidimensional Scale of Perceived Social Support (MSPSS)

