All of these measures will be collected at baseline and post-intervention.

Aim 3 will address our second objective to assess the acceptability, appropriateness, and feasibility of critical narrative development as an intervention strategy for SGM EA of color. We will conduct in-depth interviews with participants after completing the CNI (photo-novella or digital storytelling), which will assess the participants' acceptability of the critical narrative intervention. Utilizing a semi-structured interview protocol, participants will be asked questions about their experience with the intervention, including how it impacted the participant. Some sample question includes, "Tell me about your experience with creating your narrative," "What did you like (and not like) about this process," and "How has this project impacted you?"

We will also assess the acceptability, appropriateness, and feasibility of CNs for SGM EA of color utilizing several validated measures after participants complete their CN:

- 1) the acceptability of intervention measure (AIM) to assess the acceptability,
- 2) the intervention appropriateness measure (IAM) to assess the appropriateness, and
- 3) the feasibility intervention measure (FIM) to assess feasibility.

BACKGROUND:

The transition into adulthood for sexual and gender minority (SGM) emerging adults (EA; ages 18-24) in the United States, along with stressors of stigma experiences as a sexual minority and/or gender minority, may contribute to the disproportionate mental illness risk (e.g., depression, suicidal ideation, anxiety, and substance use) and decreased mental health treatment compared to their peers (Swann et al., 2020; Tan et al., 2017). These mental health differences are especially pronounced in SGM EA of color (racial/ethnic minorities; Mereish et al., 2021).

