Using online recruitment methods where the intervention is not pitched by a recruiter minimizes the risk of potential coercion. Instead, SGM EA of color can choose and click on the recruitment advertisement and decide if they wish to learn more. Similarly, staff will be trained to discuss all elements of the consent process with potential participants. Consent documents will fully explain the study procedures, potential risks, and potential benefits. Participants will also be reminded that the study participation is voluntary and that refusing to participate in the study or withdrawing from the study is an option at any time.

STUDY DESIGN:

Critical narratives have not been examined for addressing psychological outcomes (e.g., depression, anxiety, self-esteem, empowerment, psychological well-being) within SGM EA of color; therefore, this pilot study will examine the use of CNIs to impact SGM of color psychological outcomes. Prior literature has shown that CNIs have the potential to increase

empowerment, self-efficacy, and social support as a prevention strategy for mental health. The study design will utilize mixed methods to address two aims:

- Aim 1) Examine the experiences of discrimination and acceptance of SGM EA of color living with depression and its impact on seeking mental health treatment,
- Aim 2) Evaluate the change in psychological and well-being outcomes (depression, anxiety, self-esteem, empowerment, and psychological well-being) of SGM individuals of color after each CNI assignment.
- Aim 3) Understand the acceptability, appropriateness, and feasibility of critical narrative development as an intervention for SGM EA of color.

Below is a timeline of the study, including study assessments and how they address one of the three aims:

Critical Narrative Intervention Timeline and Study Design			
Month(s)	Timepoint	Measure/Study Procedure	Aim(s) Addressed
1-6	Recruitment	Eligibility Screener	N/A
2-8	Baseline	Baseline Survey (n=30) Individual Interview (n=30) Randomization Photo-novella, n=15 Digital storytelling, n=15	Aim 2 Aim 1
3-10	1-month	1-Month Follow-up Survey (n=30) Individual Interview (n=30)	Aim 2 and Aim 3 Aim 3

The entire study will last about 10 months from recruitment to final collection of all critical narratives. A participant's time in the study will last about one month from enrollment during baseline to completion of the post-intervention visit and presentation of their critical narrative.

METHODS:

1. Study Instruments:

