
Potential participants interested in participating in the study will first complete an eligibility screener. Those participants that are deemed eligible based on inclusion/exclusion criteria will be contacted by a study team member to schedule a virtual baseline visit.

Participants will complete 2 online surveys during the study: at baseline and after completion of the critical narrative development (about 1 month after initial enlistment into the study). Assessments will take 20-25 minutes to complete. The primary goal of the two surveys will be to assess the preliminary effectiveness of the critical narratives at impacting depression, anxiety, self-esteem, psychological well-being, and empowerment. All surveys will be housed and implemented through REDCap. Below is a table of the measures utilized in the surveys.

Construct	Measure	Description	Citation	Time Point	
				Baseline	1-Month
Depression Symptoms	Patient Health Questionnaire (PHQ-9)	The PHQ-9 is a 9-item depression symptom checklist scored from 0 to 3 on a Likert scale of "not at all" to "nearly every day." The PHQ-9 has demonstrated high internal reliability ($\alpha = .88$) and test-retest reliability ($\alpha = .94$)	Kroenke, K., Spitzer, R.L., & Williams, J.B. (2001). The PHQ-9: Validity of a brief depression severity measure. Journal of General Internal Medicine , 16(9), 606-613.	X	X
Anxiety Symptoms	Generalized Anxiety Disorder (GAD-7)	The GAD-7 is a 7-item measure designed to assess anxiety symptoms scored from 0 to 3 on a Likert scale of "not at all" to "nearly every day," with total scores ranging from 0 to 21. The	Spitzer, R.L., Kroenke, K., Williams, J.B., & Lowe, B. (2006). A brief measure for assessing generalized anxiety disorder: the GAD-7.	X	X

		GAD-7 is valid with intercorrelations with the PHQ-2 ($r = .64$) and the Rosenberg Self-Esteem Scale ($r = .43$) and has good reliability ($\alpha = 0.89$; Lowe et al., 2008).	Archives of internal medicine, 166 (10), 1092-1097.		

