Participants provide consent for the research team to retain email addresses and phone numbers for participant follow-up. During the baseline visit, participants will be scheduled for a 1-month follow-up visit, including an interview, survey, and final submission of the critical narrative. A week before the scheduled 1-month follow-up, a research team member will reach out to the participant to confirm the 1-month study visit via phone, e-mail, or text as indicated in the participant's preferred contact method. A research team member will reach out every two days for confirmation until received from the participant. This will aid in ensuring confirmation of the scheduled follow-up and retention of participants at the follow-up time point.

STUDY PROCEDURES:

Detailed Description:

The research activities involve a two-arm pilot enrolling a sample of 30 participants who identify as SGM, POC, and living with moderate to severe depression. After consent and completion of the baseline survey (15-20 min) and interview (45-60 min), participants will be randomized into one of two critical narrative interventions: photo-novella (n=15) or digital storytelling (n=15).

All participants will be given the same two prompts for their narrative intervention asking, "Share an experience of when you have felt seen as an SGM Person of Color." AND "share an experience of when you have felt unseen as an SGM person of color."

Photo-Novella: Participants in the photo-novella intervention will be asked to tell their story through 12 photographs and a caption (6 for the first prompt and 6 for the second prompt). Participants will be instructed to take a photograph answering the two prompts. Participants may use their smartphones or digital camera to capture their photographs. Participants may also edit their photographs using photo-editing software for aesthetics. Participants will also be asked to provide a short caption (no more than two sentences) explaining their photograph and provide a title for their work. Participants will be provided with a basic guide on photography and how to "snap a picture."

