Digital Story: Participants in the digital storytelling intervention will be asked to tell their story in 3-6 minutes (two videos total, 1-3 minutes each) utilizing a video format which can include still or moving images, sound, music, and voiceover. Participants will be provided with a guide on software or applications that they can use to create their stories. Participants will be provided with a manual or basic guide to digital stories for their reference. Participants

will be provided with guidance on expectations of the video, including format, length, quality, and closed captions for accessibility.

At the baseline visit after the survey and interview, participants will be randomized into one of the two intervention conditions (photo-novella or digital story). Once the participant is randomized, they will be provided with the electronic manual (based on their intervention). The research team member will provide guidance on what to expect (i.e., how many photos to take and what the prompt is) and go over the manual with the participant. The participant will then be given the opportunity to ask questions.

The participants will be given one month to complete their narrative and be asked to digitally submit their work to the research team during the 1-month visit. Participants will also be given the opportunity to present their work at a gallery (but not required to), which will be scheduled later (about ten months from the date of the first enrollment). The gallery and participation in the gallery are entirely voluntary and will not affect participation in the study.

A week before the scheduled 1-month follow-up, a research team member will reach out to the participant to confirm the 1-month study visit via phone, e-mail, or text as indicated in the participant's preferred contact method. A research team member will reach out every two days for confirmation until received from the participant.

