Participants will receive a link via email a day before their one-month follow-up visit to complete a follow-up survey (15-20 mins). During the one-month follow-up, a research team member virtually on Zoom will conduct a follow-up interview (45-60 mins) asking participants about their experience of creating their critical narrative piece. At the one-month follow-up, research team members will review the final critical narratives of the participants digitally. Two days before the one-month follow-up, participants will receive a link via email to a Box folder (that is HIPAA compliant) where they can upload their photos/videos.

The participants will be notified of the gallery date and invited to attend. The gallery is optional and does not impact participation in the study.

Use of Deception:

Not applicable. This study does not utilize deception.

Statistical Analysis:

Prior to conducting our multivariate analyses, we will examine study variables using descriptive statistics and test for differences across demographic characteristics (e.g., race/ethnicity, age, education) using t-tests, ANOVAs, and Chi-squares, as appropriate. As participants will be randomized to the two groups, systematic baseline differences are not expected; however, if some parameters differ across conditions at baseline, they will be included as covariates in subsequent multivariate models.

As appropriate, we will compare differences from baseline to the 1-month outcomes across our outcome measures using t-tests and Chi-squares. We will also estimate the effect size of our interventions to aid us in determining the future sample size needed for a larger study on the intervention.

Power analysis

Due to the exploratory nature of this study, a power analysis was not conducted for an a priori sample size. However, we will be conducting in-depth interviews until we reach saturation. Typical saturation for in-depth interviews is determined as between 9-17 participants (Hennink & Kaiser, 2022), therefore, we will recruit a total of 30 participants (15 participants for each condition).

RISK/BENEFIT ASSESSMENT:

1. Risks:

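### Aim 2 and the survey goal credit critical narratives with change that no arm controls for, and the planned effect size could carry that change into the next study's sample size

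*Combined protocol and SAP*

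**What the plan says.** Aim 2 is worded in several ways.

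- Objectives, specific aim 2: "Evaluate the impact of CN on empowerment (e.g., self-esteem) and mental health outcomes (depression, anxiety, and psychological well-being".
- Outcomes: "Aim 2 will evaluate the impact of CN assignment (photo-novella or digital storytelling) in its ability to address the primary outcomes of", followed by the mental health and empowerment scales. The list of outcomes closes with "All of these measures will be collected at baseline and post-intervention".
- Study Design: the opening sentences again speak of critical narrative interventions having an impact on psychological outcomes, but the aim itself reads "Evaluate the change in psychological and well-being outcomes (depression, anxiety, self-esteem, empowerment, and psychological well-being) of SGM individuals of color after each CNI assignment".
- Methods, Study Instruments: "The primary goal of the two surveys will be to assess the preliminary effectiveness of the critical narratives at impacting depression" and the other primary outcomes.

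On the design, the Detailed Description says "All participants will be given the same two prompts for their narrative intervention", and "At the baseline visit after the survey and interview, participants will be randomized into one of the two intervention conditions". No arm without a narrative is described.

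The Statistical Analysis section plans t-tests and Chi-squares on differences from baseline to 1 month. It mentions multivariate models, not otherwise specified, that adjust for parameters differing between conditions at baseline. It ends with "We will also estimate the effect size of our interventions to aid us in determining the future sample size needed for a larger study". No contrast, standardiser or confidence interval is given for that effect size.

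**The concern.** A pilot without an untreated arm is a legitimate choice for exploratory work. The difficulty lies in what the text says the pilot will show. If everyone makes a narrative, the data cannot separate the effect of making one from whatever else happens in a month. Specific aim 2, the survey goal and the opening of Study Design nevertheless attribute the change to the narrative.

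Two things are at stake. A favourable one-month change could be reported as an effect of critical narratives. And the effect size meant to help size a larger study could be that same uncontrolled change, used as though it were a difference against a comparator.

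**Working it through.** **The plan's own figure.** The sample size is 30 (15 + 15). It rests on interview saturation at 9 to 17 participants, and 15 lies in that range. No power analysis was done, so there is no power-based number to reproduce. At the expected retention of 80%, 0.8 × 30 = 24 remain, or 12 per arm if losses are equal (assumed).

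**What each contrast can estimate.**

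| Contrast | Randomised? | What it contains |
|---|---|---|
| Photo-novella vs digital story | Yes | Difference between formats |
| Baseline to 1 month, per arm or pooled | No | Narrative effect + natural course + regression to the mean + any interview effect |
| Narrative vs no narrative | Not in the design | Not estimable |

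Specific aim 2 and the survey goal correspond to the third row. The Study Design wording of Aim 2 corresponds to the second. The Outcomes wording, which refers to assignment, could mean the first or the second.

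**Regression to the mean.** Entry requires PHQ-9 ≥ 10 (Key Inclusion Criteria), and PHQ-9 is a primary outcome. Assume a normal screened population with mean m and SD s, and a one-month correlation r, with the same score serving for entry and baseline. With no intervention effect the expected fall is s(1 − r)λ, where a = (9.5 − m)/s and λ = φ(a)/(1 − Φ(a)).

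- m = 8, s = 5.5, r = 0.60: λ = 0.979; fall = 5.5 × 0.40 × 0.979 = 2.15 points, or 0.47 SDs of change.
- m = 10, s = 6, r = 0.75: λ = 0.746; fall = 6 × 0.25 × 0.746 = 1.12 points, or 0.27.
- m = 12, s = 6, r = 0.94 (the test-retest value in the instruments table): λ = 0.553; fall = 6 × 0.06 × 0.553 = 0.20 points, or 0.10.

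The values of m and s, and the lower values of r, are assumptions. If a separate PHQ-9 is taken at the baseline survey, part of this fall occurs before baseline.

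**Precision by contrast.** Noncentral-t 95% CIs for an assumed observed effect of 0.5:

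| Contrast | Full sample | 80% retained |
|---|---|---|
| Pooled pre-post (SDs of change) | 0.12 to 0.88 (n=30) | 0.07 to 0.92 (n=24) |
| Pre-post, one arm | -0.05 to 1.03 (n=15) | -0.11 to 1.09 (n=12) |
| Between formats (d) | -0.23 to 1.22 (15 per arm) | -0.32 to 1.31 (12 per arm) |

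**Standardiser.** With equal SDs at both times, a pre-post effect in change-score SDs converts to baseline SDs by the factor √(2(1 − r)). For 0.5 this gives 0.50, 0.39 and 0.32 at assumed r = 0.5, 0.7 and 0.8. The same data can thus yield different effect sizes.

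**Illustration of sizing.** Assume a controlled successor, a true d of 0.3, and non-specific improvement of 0.1, 0.2 or 0.3 baseline SD included in the planning effect. For a two-sided t-test at alpha 0.05 and 80% power:

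| Planning effect | n per arm | True power at d = 0.3 |
|---|---|---|
| 0.3 (true) | 176 | 80% |
| 0.3 + 0.1 = 0.4 | 100 | 56% |
| 0.3 + 0.2 = 0.5 | 64 | 39% |
| 0.3 + 0.3 = 0.6 | 45 | 29% |

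Non-specific worsening would oversize the study instead.

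**What can be carried forward.** For normal data the chi-square 95% CI for an SD is 0.80 to 1.34 times the estimate at n=30, and 0.78 to 1.40 at n=24. By Fisher's z, an assumed correlation of 0.7 at n=24 has a 95% CI of 0.41 to 0.86. These inputs are imprecise too, but they do not depend on attributing the change to the narrative.

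**The case against.** The documents hedge. The primary objective speaks only of potential use, the survey goal is qualified as preliminary, the study is called exploratory, and the Study Design section words Aim 2 as change. That lowers the strength of the claim but does not supply a comparator: a preliminary estimate of effectiveness still needs something to be effective against.

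The Outcomes sentence on assignment can fairly be read as the randomised format contrast, for which causal wording is proper. That stands, so it needs clarifying and is not an overclaim. Measuring at baseline and post-intervention does not settle the reading, since it also suits a comparison of change between arms.

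The effect-size sentence directly follows the baseline-to-1-month comparison, so pre-post is its natural meaning. This narrows the ambiguity. Leaving out a confidence interval in a short exploratory plan is missing detail, not an error in itself.

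The interview route is weak. The Benefits section says only that the interview or the narrative activity may bring relief. The procedures list the survey before the interview, but do not state that it is always finished first.

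A reader might infer that the pilot needs a control arm, or that the next trial will be underpowered. The documents support neither. The pilot's purpose does not require a control. The larger study's comparator is not named, and the effect size is only to aid its sizing. If that study compared formats, the between-format estimate would be the relevant one, and its weakness would be precision.

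**Conclusion.** The concern holds as a matter of claim and planning input. Specific aim 2, the survey goal and the opening of Study Design promise an effect that the design cannot estimate. The effect size, most naturally pre-post, is an unsound planning effect for a controlled successor.

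This conclusion rests on the text: same prompts, two narrative arms, none without. The size of any bias is not known. The PHQ-9 fall of 0.2 to 2.2 points shows only that a non-zero change can arise with no narrative effect, under the stated assumptions. The 100, 64 or 45 per arm instead of 176 are illustrations under an assumed drift and an assumed controlled successor, and should not drive severity. No stated number is wrong. Severity is the low end of should-fix, with high confidence in the wording problem and much less in the downstream consequence.

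**What to change.** (a) In specific aim 2, the survey goal in Study Instruments and the opening of Study Design, adopt the Study Design wording of Aim 2, that is, change after each assignment. In Outcomes, say whether the assignment sentence means the format contrast or pre-post change. State once that the study does not estimate narrative versus no narrative, and that photo-novella versus digital story is the only randomised contrast.

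(b) In Statistical Analysis, report pre-post change (per arm and pooled) and the between-format difference separately and descriptively, each with its standardiser and 95% CI. Do not use the pre-post effect as the planning effect for a controlled study. Carry forward the outcome SD and the baseline-to-1-month correlation, each with its CI, together with retention.

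The cost is wording and reporting only: no added participants and no design change. The stated claim becomes less favourable, and the pilot no longer hands a ready-made planning effect to a controlled trial.
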